4 SPECIFIC AIMS

The purpose of this study is to establish baseline data regarding the institutional reintubation rate in a specific, high-risk patient population of interest and to determine the preliminary effectiveness of a standardized intermittent NIV/HFNC protocol in patients considered high risk for reintubation. This is a prospective, non-randomized exploratory trial with the following specific aim(s):

Aim 1. Compare reintubation rates (within 72 hours) between patients that undergo a standardized, intermittent NIV/HFNC protocol and a historical control cohort.

Aim 2. Determine whether reintubation rates differ as a function of age, gender, co-morbidity, reason for intubation, service line/operative status, or modified RSBI.

Secondary aims include calculating length of stay (ICU and total hospital), total ventilator time, in-hospital mortality rate, adverse event rates, and 30-day readmission rate. The overall demographics of the interventional group will also be compared to the historical control cohort.

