6.3 Participant Identification Procedures and Eligibility Criteria

6.3.1 Historical Control Group:

Reintubation rates are tracked at the institutional level as part of quality assessments; a delegated member of the study team will utilize this patient list to generate a study-specific subset of high-risk patients who were mechanically ventilated between February and October 2019. This list will be screened for the inclusion/exclusion criteria below by a delegated member of the study team. The study statistician or designee will then use a random number generator to generate a final group of 80 patients that meet inclusion criteria.

Inclusion Criteria

1. Age ≥ 18 years
2. Chronic cardiac or pulmonary condition
 - o COPD, history of based on any documentation notes
 - o CHF, history of based on any documentation notes
 - o Positive fluid balance, defined as a positive number when calculating fluid input minus fluid output over the approximate 24-hour-period prior to extubation
3. Documented modified RSBI between 58-105 on the day of extubation

Exclusion Criteria

1. Patients receiving comfort care or terminal extubation
2. Home ventilator, based on any documentation notes
3. Only primary extubations will be included (i.e., if the patient list query identifies multiple mechanical ventilations, only the primary encounter/event will be included)

6.3.2 Prospective Group:

An EMR-based report of all patients that have been on mechanical ventilation (MV) at Grant Medical Center for at least 24 hours will be generated daily (Monday through Friday), per standard procedure. Eligibility determination for this cohort will be conducted by a delegated member of the study team across two time points: pre-screening to determine eligibility to approach for consent, and eligibility on the day of extubation to determine enrollment eligibility (Appendix A). Only patients meeting all required eligibility criteria above will be enrolled to the study; any PHI collected for patients that are not subsequently enrolled will be destroyed after non-eligibility determination.

Pre-Screening Criteria:

1. No home ventilator, based on any documentation notes
2. Not scheduled for terminal extubation/comfort care
3. Has not had a failed extubation during the current hospital stay
4. Has not previously participated in the current trial

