7.1 Statistical Analysis Plan

In general, categorical variables will be summarized with counts and percentages; and continuous variables will be summarized with means, standard deviations, medians and ranges. The two groups will be compared on categorical variables using chi-square tests, or Fisher's exact tests if the data in the contingency table have cells with expected frequency of $n < 5$. The two groups will be compared on the continuous variables using a t-test if the variable is approximately normally distributed or using a Wilcoxon rank sum test if the variable is markedly non-normally distributed. These general statistical methods will be used to compare groups on all the demographics and baseline characteristics, for the intention to treat (ITT) and per protocol (PP) populations.

Results will be considered statistically significant if the p-value is less than or equal to 0.05. SAS V9.3 or higher will be used for all summary statistics and statistical analyses.

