7.1.1 Primary Statistical Analysis Methods

Because this is a non-randomized study, it is assumed that there will be some differences between groups on the demographics and/or baseline characteristics. Therefore logistic regression modeling

techniques will be used for the primary statistical analyses. This will allow for comparison of the groups on reintubation rate while adjusting out baseline differences.

The primary analysis is comparison of the groups on reintubation rates within 72 hours on the ITT population. Potential differences between groups on demographic and baseline characteristics will be adjusted for in the model by including any statistically significant demographic and baseline characteristics as covariates in the logistic regression model.

Additional primary analyses include:

Re-intubation required (no/yes)

- a. Within 24 hours
- b. From 24-48 hours
- c. From 48-72 hours
- d. >72 hours but ≤ 7 days

The same methods used for the primary analyses will be repeated for these additional primary outcomes (within 24, 24-48, 48-72, and >72hrs) for the ITT population; and these analyses will also be repeated for the PP population (within 24, 24-48, 48-72, and >72hrs).

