7.1.2 Secondary Statistical Analysis Methods

Total hospital length of stay, ICU length of stay, ventilator time, in hours, will be compared between groups using Wilcoxon rank sum tests, as the durations are expected to be markedly non-normally distributed and skewed.

In-hospital mortality and 30-day readmission rates will be compared between the groups using a chi-square test, or Fisher's exact test if the data in the 2x2 contingency table have cells with expected frequency of $n < 5$.

All secondary analyses will be completed on the ITT population.

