7.1.3 Safety Analysis Methods

Details on adverse events will be collected. No formal statistical analyses are planned for the safety data, but summary statistics (counts and percentages) within each group will be tabulated based on ITT.

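### Secondary outcomes are compared without adjustment in a non-randomised study, and the 24-hour ventilation minimum is stated for the prospective group only

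*Combined protocol and SAP*

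**What the plan says.** Section 7.1.1 gives the reason for adjusting the reintubation comparison: "Because this is a non-randomized study, it is assumed that there will be some differences between groups". It then uses logistic regression with baseline covariates.

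Section 7.1.2 turns to the same two groups. The three duration outcomes "will be compared between groups using Wilcoxon rank sum tests, as the durations are expected to be markedly non-normally distributed and skewed". For the binary outcomes, "In-hospital mortality and 30-day readmission rates will be compared between the groups using a chi-square test", with Fisher's exact test for small expected counts. No covariates, matching or regression are named for any of the five. The general rule in Section 7.1 covers them: "Results will be considered statistically significant if the p-value is less than or equal to 0.05".

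Adverse events are treated differently. Section 7.1.3 states that "No formal statistical analyses are planned for the safety data", so they are outside this point.

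On entry to the cohorts, Section 6.3.2 identifies prospective patients from "An EMR-based report of all patients that have been on mechanical ventilation (MV) at Grant Medical Center for at least 24 hours". Section 6.3.1 takes controls from an institutional quality list, narrowed to "high-risk patients who were mechanically ventilated between February and October 2019". Neither that text nor the control inclusion and exclusion criteria set a minimum time on the ventilator, and the list's own entry rule is not given.

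**The concern.** The plan's reason for adjusting reintubation applies equally to length of stay, ventilator time, mortality and readmission. Testing those outcomes without adjustment at the 0.05 level lets a difference in case mix be reported as a significant result, or shifts an estimate without any significant p-value. Section 3.1 says the data will be used to plan a randomised trial, so a shifted estimate could be carried forward.

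The entry rule is a separate problem, and covariate adjustment would not cure it. If short ventilations are screened out of one group only, the groups differ on ventilator time by construction. Hospital and ICU stay would move in the same direction because they include the ventilated time.

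**Working it through.** **No figure to reproduce.** The plan gives no power, effect size or sample-size calculation for a secondary outcome. The check is a reading of the sections plus two illustrations.

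**1. Side by side.**

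| | Reintubation (7.1.1) | Length of stay, ventilator time, mortality, readmission (7.1.2) |
|---|---|---|
| Groups | 40 prospective v up to 80 historical | the same |
| Baseline differences expected | yes | the same groups, so yes |
| Covariates in the comparison | yes | none named |
| Significance rule | p ≤ 0.05 | p ≤ 0.05 |

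**2. What imbalance could do to mortality.** The documents give neither the size nor the direction of imbalance, so these inputs are assumed. Let a risk factor be present in 30% of one group and 50% of the other, with mortality 10% without it and 30% with it, and no treatment effect.

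- Group at 30%: 0.10 + 0.20 × 0.30 = 0.16
- Group at 50%: 0.10 + 0.20 × 0.50 = 0.20
- Apparent odds ratio: (0.20/0.80) / (0.16/0.84) = 1.31, or 1/1.31 = 0.76 if the imbalance runs the other way

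So an unadjusted comparison can look like harm or benefit when there is neither.

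**3. The one-sided 24-hour minimum.**

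Inputs: 40 prospective and 80 controls (Section 5); significance at 0.05 (Section 7.1), taken as two-sided; *f*, the share of controls ventilated for under 24 hours, assumed. Apart from the minimum, both groups have the same distribution of ventilator time.

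The Wilcoxon test uses ranks only, so ventilator time can be replaced by its percentile in the untruncated population. Controls are then uniform on (0, 1) and prospective patients uniform on (*f*, 1). A random prospective patient exceeds a random control with probability equal to the mean of the prospective percentile:

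P(prospective > control) = (1 + *f*)/2 = 0.5 + *f*/2

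The result depends on *f* alone, not on the shape of the distribution. Simulating 40 v 80 with no true effect (20,000 replicates) gives:

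| *f* (assumed) | P(prospective > control) | Rejection, minimum in prospective group only | Rejection, same minimum in both |
|---|---|---|---|
| 0% | 0.500 | 5% | 5% |
| 5% | 0.525 | 7% | 5% |
| 10% | 0.550 | 14% | 5% |
| 20% | 0.600 | 43% | 5% |

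These rates are for ventilator time. Length of stay would be affected in the same direction, but the documents give nothing from which to compute the amount.

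**4. Can *f* be bounded from the documents?** No. Section 6.4 gives a typical ventilation time of 3–5 days, but that section is headed as applying to the prospective group only. It does not say whether the figure is a mean or a median, and it may describe patients already past 24 hours. It cannot fix the share of controls below 24 hours.

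**The case against.** The strongest case is about weight. The study is exploratory, and Section 4 words the secondary aims as "calculating length of stay (ICU and total hospital), total ventilator time, in-hospital mortality rate" and so on, which is closer to description than to testing. Section 7.1 compares the groups on all baseline characteristics, so measured imbalance will be visible. Section 6.1 records the controls' oxygen management so that later analyses can account for it. These points limit the consequence, but none supplies an adjusted method for a secondary outcome, and Section 7.1.2 does specify tests.

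On the entry rule, the 24-hour figure belongs to a routine daily report and is not a numbered eligibility criterion, and the quality list may carry an equivalent minimum. That stands: the bias is conditional. The report still decides which prospective patients can be screened.

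A further objection is that adjustment will be weak. With 12–24 deaths (10–20% of 120, assumed) and four coefficients there are 3–6 events per coefficient. That also stands. It argues for a small, prespecified covariate set and a penalised model.

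A reader might infer that, because the protocol acts only after extubation (Section 9.2), the named length-of-stay and ventilator-time endpoints are invalid and should be replaced by measures that start at extubation. The documents do not support that. Sections 2.1 and 4 name total stay and total ventilator time as endpoints, and Appendices A and F, whose content is not in the text reviewed, may define the clock. Time before extubation adds noise, and bias only if the groups differ on it. Replacing the endpoints would be a change of question.

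**Conclusion.** The inconsistency is real: one adjustment rule for reintubation and none for five secondary outcomes in the same non-randomised groups. The unequal ventilation minimum is real as written, and its effect depends on an unknown. If no minimum operates for controls, false rejection on ventilator time is about 7%, 14% or 43% at *f* of 5%, 10% or 20%, against a nominal 5%.

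A reader might infer that the ventilator-time comparison is already known to be biased, or that the plan would produce a false benefit on it. Neither follows. The quality list's entry rule is not given, and the bias, if present, makes ventilation look longer in the prospective group. It could hide a benefit or suggest harm. For other baseline imbalance, both size and direction are unknown.

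The overall impact is modest, because these are secondary outcomes of an exploratory study. The change is still worth making because it is cheap and the data feed a later trial. Confidence is medium.

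**What to change.** 1. **Adjusted analyses.** Add to Section 7.1.2 covariate-adjusted analyses using a small set fixed in advance from the Aim 2 variables, for example age, co-morbidity and modified RSBI. Use Firth logistic regression for mortality and readmission, and proportional-odds regression for ICU and hospital stay, stating how in-hospital deaths are handled. Keep the Wilcoxon and chi-square/Fisher tests and label them descriptive.
2. **Common minimum.** Apply the same 24-hour ventilation minimum to historical controls before the random selection, or state that the quality list already has it.
3. **Endpoints.** Keep the named length-of-stay and ventilator-time endpoints. Optionally add length of stay from the index extubation as a supplement, and tabulate pre-extubation ventilator time descriptively. State that this does not make it a candidate covariate for the primary model, because Section 7.1.1 would otherwise admit it if it differed significantly.

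**Cost.** SAP wording and a little programming. Ventilation start times must be available for controls. Control numbers look sufficient on a rough count: 80 ventilated patients a month (Section 5) × 9 months = 720; at the plan's 40-of-240 yield, 720 × 40/240 = 120 would qualify. Removing 5%, 10% or 20% leaves 114, 108 or 96, all above 80. This assumes that the prospective yield carries over to controls.

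**Downsides.** Adjusted estimates will be imprecise, and unmeasured differences remain. Weekday listing and consent before extubation may still keep short ventilations out of the prospective group, so a common minimum may not equalise the groups fully; the optional tabulation would show this.

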7.1.3 Safety Analysis Methods

Details on adverse events will be collected. No formal statistical analyses are planned for the safety data, but summary statistics (counts and percentages) within each group will be tabulated based on ITT.

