2 STUDY SUMMARY

2.1 Protocol Summary Table

Protocol Title & Number	Exploratory trial to improve postextubation management for patients at risk for extubation failure IRB# 1332767
Study Short Title	GMC – [name] – Postextubation Management Pilot
Research Method	Prospective Interventional
Therapeutic Area	Pulmonary/Critical Care
Department	Intensive Care Unit, Critical Care Unit, 4 East
Study Description	This is an exploratory study designed to gather baseline information to determine the effectiveness of a standardized postextubation management protocol in a subset of patients at risk for reintubation.
Primary Endpoints	
• Proportion of patients that require reintubation within 72 hours• Association between reintubation rates and patient demographics or characteristics
Secondary Endpoints	
• Length of stay (ICU and total)• Ventilator time• In-hospital mortality• In-hospital adverse event rate• 30-day readmission rate
Prospective Cohort Study Population ^a	This study will include up to 40 mechanically ventilated, adult patients considered at-risk for re-intubation. See Section 6.3 . for detailed inclusion criteria.
Intervention(s)	
• Early NIV via BiPAP• High Flow Nasal Cannula breaks from NIV• Wean after 24 hours
Duration	Intervention Duration – Approximately 24 hours Study Duration – 3 months Participant Duration- total hospital stay, estimated at 14.1 ± 16.9 days (American Association for the Surgery of Trauma, 2011).

^a Data for this study will be compared to a historical control cohort, comprising mechanically ventilated, high-risk patients who underwent standard of care postextubation management.

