5 STUDY POPULATION AND SAMPLE SIZE

There are approximately 3-4 patients per business day (Monday through Friday) that require mechanical ventilation at OhioHealth Grant Medical Center, resulting in approximately 80 patients per month. An estimated 30% of these patients are high risk, resulting in an estimated 24 high-risk patients per month.

A historical control cohort will consist of up to 80 randomly selected high-risk patients that underwent planned extubation in an OhioHealth Grant Medical Center Intensive Care Unit prior to initiation of the prospective cohort.

For the prospective, interventional cohort we plan to consent all adult mechanically ventilated patients that meet pre-screening criteria in order to obtain a final sample size of 40 enrolled patients who meet all criteria on the day of extubation. We anticipate this will result in up to 240 patients consented and 40 patients enrolled over approximately 12 weeks; however, this time period can be extended if needed to obtain 40 patients in the final data set.

See [Section 6.3](#) for detailed inclusion/exclusion criteria.

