6.8 Study Limitations

A potential limitation of this study is that participants for whom informed consent is obtained may not be representative of the population as a whole, which would limit the generalizability of the data. The extent to which demographics of those enrolled differ from the population as a whole will be assessed as outlined in [Section 7.1](#).

7 Data Collection, Handling & Record Keeping

With the exception of source data recorded using the Postextubation Management Worksheet (Appendix G), all study data will be recorded directly from electronic medical records into the study-specific REDCap database (Appendix A for prospective cohort data and Appendix F for historical control cohort). Research Electronic Data Capture (REDCap) is a secure web application for building and managing online surveys and databases. The REDCap program and the resulting data are maintained on internal servers and backed up regularly. REDCap has the technical capabilities to be HIPAA and 21 CFR 11 compliant.

The Postextubation Management Worksheet will be maintained at the patient's bedside until completed, at which point the data will be entered into REDCap and the paper files will be given to OhioHealth Research Institute.

The data collection and storage processes will follow HIPAA guidelines and OhioHealth policy to protect both confidentiality and privacy of each participant. Paper files will be stored in a secure facility with limited access (e.g., the offices of the OhioHealth Research Institute) and electronic files will be stored within the OhioHealth network, under password protection and encryption. All PHI data will be destroyed at the end of the study and only de-identified data will be maintained.

Per Health and Human Services Federal Regulations, research-related documents will be maintained for at least three years after completion of the research. All research-related documents (e.g., informed consent forms, data collection forms, electronic spreadsheets) will be provided to OHRI for retention.

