9.2 Adverse Events

An adverse event is any untoward or unfavorable medical occurrence in a human subject, including any abnormal sign (e.g. abnormal physical exam or laboratory finding), symptom, or disease, temporally associated with the subject's participation in the research. As outlined above ([Section 9.1](#)), AEs that are unexpected, related or possibly related to the research *and* suggest increased risk will be reported to the OhioHealth IRB.

It is possible that research participants may experience adverse events that do not meet OhioHealth's mandatory reporting requirements (e.g., they are not unexpected, they are not possibly related to participation in the research, they do not place the subjects or others at greater risk of harm). Adverse events that do not meet reporting requirements will be reported to the Data Safety Monitoring Board (DSMB) for review during standing DSMB meetings and summarized for the IRB during the continuing review.

Importantly, for the current study, adverse events associated with mechanical ventilation cannot be related to the study intervention, as study-specific interventions do not occur until the patient is extubated. As such, mechanical ventilation-related adverse events that occur prior to the day of planned extubation will not be reported to the OhioHealth IRB.

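### Adverse event percentages are tabulated for both groups, but the text sets no definition, start time or capture method that fits both

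*Combined protocol and SAP*

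**What the plan says.** - **Endpoint.** Section 2.1 lists "In-hospital adverse event rate" among the secondary endpoints. A footnote to that table says the study's data will be set against a historical control cohort. Section 4 states the aim as one of calculation: "Secondary aims include calculating length of stay (ICU and total hospital), total ventilator time, in-hospital mortality rate, adverse event rates, and 30-day readmission rate".
- **Analysis.** Section 7.1.3 rules out formal testing of the safety data and adds that "summary statistics (counts and percentages) within each group will be tabulated based on ITT". Section 7.1.2 names the secondary outcomes to be tested between groups (stays, ventilator time, mortality, readmission); adverse events are not among them.
- **Definition.** The only adverse event definition in the text is in Section 9.2, under event reporting. It covers untoward medical occurrences "temporally associated with the subject's participation in the research".
- **Controls.** Section 6.3.1 draws them from "high-risk patients who were mechanically ventilated between February and October 2019", and Section 5 requires their extubation to fall "prior to initiation of the prospective cohort".
- **Data capture.** Under Section 7, data for both cohorts come from the electronic record, on separate forms (Appendix A for prospective patients, Appendix F for controls). The exception is data on the bedside Postextubation Management Worksheet (Appendix G). Section 6.7 schedules that worksheet for study days 0 to 2.
- **Oversight.** The DSMB reviews prospectively enrolled patients (Section 8.2). The investigator judges expectedness and relatedness to the research (Section 9.1). Serious events go to the DSMB (Section 9.3).
- **Limitations.** Section 6.8 mentions only whether consented patients are representative.

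**The concern.** Two columns of percentages in a study built around a historical comparison will be compared, with or without a p-value. For that reading to be fair, an event has to mean the same thing, be counted over the same period and be looked for in the same way in both groups. The text secures none of the three.

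At stake is the safety message carried forward. Section 3.1 says the study is meant to supply preliminary data for planning a larger randomised trial. An apparent excess of events on the NIV/HFNC protocol, or an apparent reassurance, could come from how events were found rather than from the protocol itself. Table 1 in Section 8 makes this plausible. Its BiPAP/HFNC column includes mild complaints such as dry mouth and claustrophobia, which depend on someone asking and writing them down. Its ventilation column includes events that can occur before extubation.

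**Working it through.** The plan gives no adverse event rate, capture rate or sample-size figure for this endpoint, so there is no figure to reproduce. The check is mainly a comparison of what the text provides for each group.

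| | Prospective (up to 40) | Historical control (up to 80) |
|---|---|---|
| Definition (9.2) | Linked in time to research participation | Never participated; no other definition given |
| Start of counting | Not set at extubation; only in-hospital | Not set at extubation; only in-hospital |
| Record abstraction (7) | Yes, Appendix A form | Yes, Appendix F form |
| Bedside worksheet (6.7, 7) | Days 0 to 2 | None |
| Investigator and DSMB review (8.2, 9.1, 9.3) | Yes | None |

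**Definition.** The Section 9.2 wording cannot be applied as it stands to up to 80 of 80 + 40 = 120 patients. Abstractors would need a rule that the text does not state.

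**Start time.** Section 9.2 says ventilation-related events cannot be related to the intervention because the intervention begins only after extubation. It then excludes such events before the day of planned extubation from IRB reporting, but not from the endpoint table. Under the participation definition, a prospective patient's count could begin at enrolment on study day 0 (Sections 6.6 and 6.7). A control has no corresponding date, so the whole stay could be read. Conversely, if the whole stay is read in both groups, the prospective list comes from patients ventilated for at least 24 hours (Section 6.3.2), while the control criteria state no such minimum. The effect could go either way.

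**Hypothetical illustration.** None of these inputs comes from the documents. Take the rate as the percentage of patients with at least one event. Let the true post-extubation rate be 30% in both groups, with 90% captured prospectively and 80%, 70% or 50% captured in controls.

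Observed rate = true rate × capture.

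- Prospective: 0.30 × 0.90 = 0.27, or 10.8 of 40.
- Control, 80% capture: 0.30 × 0.80 = 0.24, or 19.2 of 80. Gap 3 points; ratio 0.90/0.80 = 1.125.
- Control, 70% capture: 0.30 × 0.70 = 0.21, or 16.8 of 80. Gap 6 points; ratio 0.90/0.70 = 1.29.
- Control, 50% capture: 0.30 × 0.50 = 0.15, or 12.0 of 80. Gap 12 points; ratio 0.90/0.50 = 1.80.
- Equal capture: 0.90/0.90 = 1.00.

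The ratio depends only on capture, not on the assumed true rate.

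Now suppose that pre-extubation events were counted in controls only, in patients with no other recorded event. The apparent excess would reverse once they added more than 3, 6 or 12 points respectively, that is, more than 0.03 × 80 = 2.4, 0.06 × 80 = 4.8 or 0.12 × 80 = 9.6 control patients. A small difference in the counting rule is enough to change the sign.

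**The case against.** The strongest reply is that the plan makes no between-group safety inference. Section 7.1.3 is descriptive, Section 4 speaks of calculating rates, and Section 7.1.2 leaves adverse events out of its tests. That is right. A reader might infer that the SAP builds in a biased safety comparison; it does not. What remains is the risk of a misleading side-by-side table.

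Second, the Section 9.2 definition governs reporting to the IRB and DSMB, and nothing says it defines the endpoint. A reader might infer that controls have a zero rate by definition. Section 7.1.3 plainly intends a count in each group, so that reading fails. It still leaves the endpoint without a stated definition for controls.

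Third, most data in both cohorts come from the same electronic record, and Appendices A, F and G were not available. Forms A and F may share a checklist, and it cannot be verified that the worksheet records adverse events at all. Relatedness and DSMB review classify and report events; the text does not say they add any. So unequal ascertainment is a possibility, not an established fact.

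Fourth, nothing confines pre-extubation events to controls. Some device-related events may also be truly rarer in controls, because fewer received the devices. Both points stand, and both are reasons not to claim a direction.

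**Conclusion.** The point holds as a cheap improvement to a descriptive table. The text gives no adverse event definition that fits the controls and no start at extubation for either group. It also gives the prospective group a worksheet and oversight that controls lack. The two percentages may therefore differ for reasons unrelated to the intervention, and Section 6.8 does not warn of this.

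The stronger statements, that the endpoint is not comparable or that the intervention rate will be inflated, go beyond the documents. Direction and size cannot be derived from them. The gaps of 3 to 12 points shown above rest wholly on an assumed 30% true rate and assumed capture of 90% against 50% to 80%. If Appendices A and F already hold the same event list and window, a sentence in the SAP saying so would settle most of the matter.

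**What to change.** In Section 7.1.3, base the two-group adverse event table on one fixed list of chart-identifiable events (for example death, pneumonia, tracheostomy, lung injury). Count them from extubation to discharge and abstract them from the electronic record in the same way for both groups. State that this list, not the Section 9.2 reporting definition, defines the endpoint. Report worksheet-captured events and BiPAP/HFNC tolerance events for the prospective group only, in a separate table. In Section 6.8, add that adverse event ascertainment may differ between the groups.

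The cost is SAP wording and a shared abstraction list, with no extra patients or procedures. The downside is that fewer event types appear in the two-group table.
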